**Efficacy and Safety of High Dose Tamoxifen to Advanced Hormone Receptor-  
High Expressed Endocrine Therapy Resisted Breast Cancer: A Single-arm Phase  
II Pilot Trial**

NCT number: NCT03045653

Study Institution: Sun Yat-Sen University Cancer Center, State Key Laboratory of  
Oncology in South China, Collaborative innovation center for Cancer Medicine

Protocol Version: v 2.0

Date: 2018-01-10

**Protocol Synopsis:** This study conducted a single arm open label phase 2 trial. Patients received treatments of 100 mg/d tamoxifen. The primary endpoint was the progression-free survival (PFS). Secondary endpoints included objective response rate (ORR), clinical benefit rate (CBR), overall survival (OS) and safety. Exploratory endpoints included the efficacy predictive value of the 18F-FES SUVmax.

**Inclusion Criteria:**

Eligible patients were 18-70 years old females with pathologically or histologically confirmed MBC and high expression of ER or progesterone receptor in metastatic or primary tumor lesions (immunohistochemical staining: ER-positive cells  $\geq$  60% and/or progesterone receptor-positive cells  $\geq$  60%). Patients had disease that progressed  $\geq$  12 months after adjuvant endocrine treatment or after receiving standard endocrine salvage treatment. Patients had an Eastern Cooperative Oncology Group performance status of 0 or 1. MBC had to be measurable by Response Evaluation Criteria in Solid Tumors (RECIST) version 1.1 or had to be immeasurable bone-only disease. For patients who planned to undergo baseline 18F-FES PET/CT examination, discontinuation of TAM for  $\geq$  2 months was required to avoid the blockade of the imaging agent.

**Exclusion Criteria:**

The exclusion criteria included primary ET resistance (disease relapsed within the first 2 years of neoadjuvant or adjuvant ET or progressed within the first 6 months of ET for MBC); visceral crisis; evidence or history of central nervous system metastasis.

**Interventions**

After enrollment and the signing of informed consent, patients received oral 100 mg/d TAM treatment until disease progression.

**Study Endpoints:**

The primary endpoint was progression-free survival (PFS). The key secondary endpoints included ORR (the proportion of patients with complete response [CR] or partial response [PR] per RECIST version 1.1), CBR (the proportion of patients with CR, PR or stable disease [SD]  $\geq$  6 months), overall survival (OS), safety and tolerability. The exploratory endpoints included the predictive value of the F-FES maximum standardized uptake value (SUVmax) of F-FES PET/CT on the efficacy of high-dose TAM therapy.

Response evaluation criteria for a single lesion: referring to the RECIST 1.1 standard, we defined the response evaluation criteria for a single lesion. Progressive disease (PD): the maximum diameter of a single metastasis lesion increased by more than 20%; CR: disappearance of target lesions; PR: the maximum diameter of the lesion decreased by more than 30%; the rest were considered SD. The definition of clinical benefit of a single lesion: according to the response evaluation criteria for a single lesion, CR, PR, or SD  $\geq$  6 months was defined as clinical benefit of a single lesion.

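### The single-lesion response scale defaults lesions without a measurable diameter to SD and has no not-evaluable class, which could distort the exploratory FES lesion analysis

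*Combined protocol and SAP*

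**What the plan says.** Study Endpoints sets out a response scale for individual lesions, adapted from RECIST 1.1.

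- **PD:** "Progressive disease (PD): the maximum diameter of a single metastasis lesion increased by more than 20"%. No other route to PD is given.
- **CR:** "CR: disappearance of target lesions".
- **PR and the residual class:** "PR: the maximum diameter of the lesion decreased by more than 30%; the rest were considered SD".
- **Benefit:** CR, PR, or SD of at least "6 months was defined as clinical benefit of a single lesion".

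The scale has no class for lesions that cannot be evaluated and no qualitative criterion for progression.

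The Inclusion Criteria require disease measurable by RECIST 1.1, with one alternative: "or had to be immeasurable bone-only disease". The same section describes a baseline FES PET/CT for patients who plan to have one, and does not exclude the bone-only patients from it.

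The exploratory endpoint is the value of FES SUVmax for predicting an effect "on the efficacy of high-dose TAM therapy". It does not say whether the unit is the lesion or the patient. Statistical Analysis names t-tests, Chi-square tests and log-rank tests. It gives no lesion-selection rule, no lesion-level model and no stratification by site.

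**The concern.** A lesion with no measurable diameter cannot show a percentage rise or fall in diameter. Read literally, the scale therefore makes it SD unless it disappears, even when it has plainly worsened. Failure is then reachable for a measurable soft-tissue lesion but hardly reachable for a non-measurable bone lesion.

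Two consequences could follow for the FES work. The lesion benefit rate may be too high at the non-measurable sites. And if SUVmax tends to differ between bone and soft tissue, the scoring rule alone could produce an association between SUVmax and lesion benefit, which would be read as FES predicting efficacy. The planned tests include no stratification by site, so nothing later in the analysis would remove it.

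**Working it through.** **No figure to reproduce.** The documents give no lesion count, lesion benefit rate or power statement for the FES analysis. The check is to apply the written rules to a non-measurable lesion, then to illustrate the possible size with assumed inputs.

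**Step 1: apply the rules to a non-measurable lesion that worsens.**

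- PD needs a diameter rise above 20%: cannot be met.
- PR needs a diameter fall above 30%: cannot be met.
- CR needs disappearance: not met.
- Result: it falls into the remainder, SD.
- Benefit: only if that SD lasts at least 6 months.

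**Step 2: assumed inputs (none is in the documents).**

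- Half of the FES lesions are non-measurable bone, half measurable soft tissue.
- True progression before 6 months is p = 0.30 at every site and every SUVmax, so SUVmax has no true effect.
- SUVmax is high in 70% of bone and 40% of soft-tissue lesions.
- f is the fraction of truly worsened bone lesions carried as SD to 6 months. It is varied from 0 to 1.

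**Step 3: bone share by SUVmax group.**

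- High: 0.7 / (0.7 + 0.4) = 0.636
- Low: 0.3 / (0.3 + 0.6) = 0.333

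**Step 4: scored benefit.** In a group with bone share s, scored benefit = 1 − p × (1 − f × s). The true value is 1 − 0.30 = 70%. Overall, s = 0.5, so the inflation is 0.30 × 0.5 × f.

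| f | High SUVmax | Low SUVmax | Odds ratio | Overall benefit | Inflation |
|---|---|---|---|---|---|
| 1 | 1 − 0.30 × 0.364 = 89.1% | 1 − 0.30 × 0.667 = 80.0% | 2.04 | 85.0% | 15 points |
| 0.5 | 1 − 0.30 × 0.682 = 79.5% | 1 − 0.30 × 0.833 = 75.0% | 1.30 | 77.5% | 7.5 points |
| 0.25 | 1 − 0.30 × 0.841 = 74.8% | 1 − 0.30 × 0.917 = 72.5% | 1.12 | 73.75% | 3.75 points |
| 0 | 70.0% | 70.0% | 1.00 | 70.0% | 0 |

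**Step 5: sensitivity to the other inputs.**

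- Weaker site difference (60% and 50% SUVmax-high), f = 1: bone shares are 0.6 / 1.1 = 0.545 and 0.4 / 0.9 = 0.444, benefit is 86.4% and 83.3%, odds ratio 1.27.
- SUVmax unrelated to site: odds ratio 1.0 at any f, but the overall rate is still inflated by 15 × f points.
- True progression of 20% or 40%, with the 70/40 split and f = 1: odds ratio 1.96 or 2.14.

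The result depends little on p. It depends heavily on f and on the site difference in SUVmax, and the documents give data on neither.

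**The case against.** **The scale may cover measurable lesions only.** It is modelled on RECIST 1.1 and its CR clause speaks of target lesions. Admitting patients with non-measurable bone disease does not by itself put their lesions on this scale. This stands as a real ambiguity. But the PD clause refers simply to a single metastatic lesion, and the scope is never stated, so two analysts could build different lesion sets.

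**No lesion-level FES analysis is specified.** This is correct: the link is an inference. It is a reasonable one, because the single-lesion definitions follow directly after the FES endpoint and no other listed endpoint uses them. ORR is a RECIST 1.1 proportion of patients, and CBR is also counted by patient.

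**SD must last at least 6 months.** A reader might infer that every worsening bone lesion is automatically credited with benefit. The documents do not support that. Under Interventions, treatment ends at progression, so a lesion in a patient who progresses early may never accrue 6 months of SD. In bone-only disease the lesion may itself drive patient-level progression, and f could be close to 0. The objection carries less weight for a patient who is eligible through measurable disease and also has a bone lesion, since patient-level status need not follow that one lesion.

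**Lesions not re-imaged.** The remainder clause could be read as making these SD too. That is weaker: response criteria presuppose an assessment, and a lesion never re-imaged has no documented 6 months of SD. What remains is that no code exists for it.

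**Conclusion.** The defect in the rule is on the face of the text: the scale has no provision for lesions without a measurable diameter, no not-evaluable class, and a remainder clause that, applied literally, grades a worsening non-measurable lesion as SD.

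Bias in the FES result is a conditional risk. It requires that such lesions enter the analysis, that a material share of those that worsen are carried as SD to 6 months, and, for a spurious association, that SUVmax differs by site. A reader might infer that the FES analysis is shown to be biased, or that an odds ratio near 2 is the expected distortion. Neither follows. That figure is the upper bound at f = 1 for an assumed 50% bone share and 70/40 split; it falls to 1.3 at f = 0.5 and to 1.0 at f = 0.

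Severity is low. The FES endpoint is exploratory, ORR is defined separately, and nothing ties this scale to PFS.

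**What to change.** In Study Endpoints:

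1. Restrict the diameter-based single-lesion scale to lesions measurable by RECIST 1.1 at baseline and re-measured at follow-up.
2. Redefine SD as measured lesions that meet none of the other criteria, in place of the open remainder.
3. Code lesions without a follow-up measurement as not evaluable.
4. State that the main FES lesion analysis uses measurable lesions, and report non-measurable bone lesions separately, for example as CR, non-CR/non-PD or unequivocal progression.

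Items 1 to 3 close the gap in the definition. Item 4 keeps a site effect from being mistaken for an SUVmax effect.

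The cost is a change of wording and one additional table from scans already taken. The downside is fewer lesions in the main exploratory analysis and possibly a lower reported lesion benefit rate.

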## **Statistical Analysis**

The primary endpoint of PFS was determined based on an intention-to-treat set. If no PFS event was observed before the cutoff date, the last tumor assessment date was defined as censored. Safety was analyzed based on a safety analysis set defined as all patients who received at least one dose of high-dose TAM and had at least one posttreatment safety assessment. Median PFS was estimated with the Kaplan-Meier method and compared by log-rank tests. The comparison of continuous variables between two samples of normal distribution was performed by the t-test, and the comparison of the two categorical data was conducted with the Chi-square test.

For all analyses, a 2-tailed  $p \leq 0.05$  was considered statistically significant, and all confidence intervals used a 95% confidence level. Statistical analyses were performed by the investigators at the Cancer Center of Sun Yat-sen University using SPSS software version 20.0 (SPSS Inc.) and SAS version 9.4 (SAS Institute).

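### PFS is to be compared by log-rank tests in a one-arm trial with no groups named; base the PFS conclusion on the Kaplan-Meier median with its interval, and analyse FES SUVmax as a continuous variable with lesions clustered by patient

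*Combined protocol and SAP*

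**What the plan says.** The synopsis states "This study conducted a single arm open label phase 2 trial", the title calls it a phase "II Pilot Trial", and under Interventions "patients received oral 100 mg/d TAM treatment until disease progression". So there is one arm and one regimen.

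The Statistical Analysis section puts the primary endpoint on the ITT set ("The primary endpoint of PFS was determined based on an intention-to-treat set") and continues: "Median PFS was estimated with the Kaplan-Meier method and compared by log-rank tests". The next sentence lists two more two-group tools: "The comparison of continuous variables between two samples of normal distribution was performed by the t-test", followed by the Chi-square test for categorical data. A significance threshold of 0.05 is then set ("For all analyses, a 2-tailed" and onward), with 95% confidence intervals throughout. None of these tests is assigned to an endpoint or a pair of groups.

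Under Study Endpoints, response endpoints are separate from PFS ("The key secondary endpoints included ORR", followed by CBR, OS and safety). The value of FES SUVmax for predicting efficacy is listed as exploratory. The same section defines response and clinical benefit for a single lesion, so a lesion-level outcome exists, but no method is attached to it.

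**The concern.** A log-rank test needs two groups or a reference curve, and this plan supplies neither. The sentence stands directly after the one on the primary endpoint and under a threshold that covers every analysis. A subgroup p-value of 0.05 or less could therefore be called significant next to the primary result without having tested activity.

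The more practical problem is the SUVmax question, the one relation to efficacy that the plan commits to. If the section's tools are used as listed, SUVmax must be cut into high and low groups for the log-rank test, and lesions must be treated as independent in the t-test or Chi-square test. The first loses power or, if the cut-off is chosen from the data, inflates false positives. The second understates the variance whenever one patient contributes several lesions. At stake is a positive imaging finding that may be an artefact of the method, or a real one that is missed.

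**Working it through.** The documents give no sample size, event count, reference median or SUVmax cut-off, so there is no figure to reproduce. All numerical inputs below are assumptions, except the 0.05 level.

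**1. What can be compared.** One arm (synopsis), one regimen (Interventions), and no groups, cut-off or reference curve in any section. The only log-rank tests that can be run compare subgroups within the arm.

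**2. What such a test responds to.** Simulation with two equal subgroups, no true difference, censoring uniform over 12 to 36 months and 4,000 runs per cell. Rate of p ≤ 0.05 by true overall median PFS:

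| N | 2 months | 4 months | 8 months | 16 months |
|---|---|---|---|---|
| 20 | 6.3% | 6.3% | 6.4% | 5.3% |
| 30 | 6.9% | 5.6% | 5.9% | 5.8% |
| 40 | 5.4% | 5.7% | 5.8% | 5.1% |

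An eightfold change in overall median (16/2) leaves the rate near 5%. The test addresses a difference between subgroups, not the activity of the treatment.

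**3. SUVmax cut into groups for the log-rank test (assumed N 20 to 40).**

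- *Searched cut-off, no true association.* Simulated false positives were 26% to 28%, against about 5% for a Cox model on the continuous value. As a rough check, the large-sample Miller–Siegmund formula for a search between quantiles ε and 1 − ε is φ(z)(z − 1/z) ln[(1 − ε)²/ε²] + 4φ(z)/z. With z = 1.96, φ(z) = 0.0584 and an assumed ε = 0.25: 0.0584 × 1.450 × 2.197 + 4 × 0.0584/1.96 = 0.186 + 0.119 = 0.305. Small samples offer fewer cut-points, so a figure a little below 31% is as expected.
- *Cut-off fixed at the median, true association present.* Simulated power was 41% to 71%, against 59% to 89% for continuous Cox on the same data. The effect size was assumed, but the gap can be checked without it. A median split of a normal variable keeps about 2/π = 64% of the information, so the expected z is multiplied by √0.64 ≈ 0.798.
  - Cox power 59%: z = 1.96 + 0.23 = 2.19; 2.19 × 0.798 = 1.75; power = Φ(1.75 − 1.96) ≈ 42%.
  - Cox power 89%: z = 1.96 + 1.23 = 3.19; 3.19 × 0.798 = 2.54; power = Φ(2.54 − 1.96) ≈ 72%.

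  Both agree with the simulated 41% and 71%.

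**4. Lesion-level t-test that ignores the patient.** Assumed 20 patients, m = 3 or 6 lesions each, within-patient correlation ρ = 0.3 or 0.5 for both uptake and outcome, and no true association. Simulated false positives were 6% to 14%. The approximate variance inflation is D = 1 + (m − 1) ρₓ ρᵧ, with ρₓ = ρ. If lesion benefit is a normal variable cut at its median, ρᵧ = (2/π) arcsin ρ, which is 0.194 for ρ = 0.3 and 0.333 for ρ = 0.5. The actual level is 2[1 − Φ(1.96/√D)]:

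| m | ρ | D | Level |
|---|---|---|---|
| 3 | 0.3 | 1 + 2 × 0.3 × 0.194 = 1.116 | 6.4% |
| 3 | 0.5 | 1 + 2 × 0.5 × 0.333 = 1.333 | 9.0% |
| 6 | 0.3 | 1 + 5 × 0.3 × 0.194 = 1.291 | 8.5% |
| 6 | 0.5 | 1 + 5 × 0.5 × 0.333 = 1.833 | 14.8% |

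The approximation and the simulation agree closely. The inflation arises only if both uptake and outcome are correlated within patients.

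**5. Meaning of an association.** With no untreated or differently treated group, a relation between SUVmax and PFS may mean that high-uptake disease has a better course under any treatment, or that it benefits more from this one. One arm cannot tell these apart.

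**The case against.** The strongest reply is that the log-rank sentence sits in a generic list of two-group tools and most likely refers to exploratory subgroups. The Kaplan-Meier median with 95% CI on the ITT set is already a valid primary analysis, a pilot may stop at estimation, and SUVmax is already labelled exploratory. Much of this stands. For PFS itself the point is mainly one of clarification, and the estimate is not in doubt. It does not answer the SUVmax problem, because an exploratory label does not correct a searched cut-off or unmodelled clustering.

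Several stronger readings are tempting but not supported.

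- *That the plan will claim efficacy from a log-rank p-value.* No section says so; the wording only leaves room for it.
- *That the p-value is unaffected by how well the arm does, so that doubling every PFS time would leave it unchanged.* This holds only if censoring times double as well, and the plan censors at the last assessment before a cutoff date. With event times alone doubled and censoring fixed (medians of 4 and 8 months, N 20 to 40), p changed in 83% to 100% of simulated data sets and crossed 0.05 in 2.5% to 5.1%. With a subgroup hazard ratio of 0.5 and N = 40, the rejection rate fell from 59% to 23% as the shorter-PFS subgroup's median rose from 2 to 32 months, because events became fewer. The accurate statement is that the test does not test activity.
- *That a particular number of subgroup tests, and hence a particular overall error rate, is planned.* The documents list no splits; eligibility criteria are not an analysis list.
- *That without a benchmark the trial cannot be interpreted.* A median with its interval is a legitimate description, and ORR and CBR are separate efficacy endpoints.

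It is also fair to say that the plan does not expressly assign the t-test, Chi-square or log-rank test to SUVmax. They are, however, the only group-comparison methods it offers.

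**Conclusion.** The point holds in a limited form and is worth fixing. It is certain from the text that the trial has one arm, that the log-rank comparison has no named groups, cut-off or reference, and that such a test cannot show activity. The Kaplan-Meier median with 95% CI remains the valid primary result.

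The quantitative part concerns SUVmax. If the cut-off is searched, false positives are about 26% to 28% instead of 5%. If it is fixed at the median, power falls by about 18 points at both ends of the range (59 − 41 and 89 − 71). A lesion-level t-test without clustering has a false-positive rate of 6% to 14%. These sizes rest on assumed patient numbers, lesion counts, correlations and effect sizes, none of which the documents give. They also assume that the listed tools would be used for SUVmax. The direction of each effect does not depend on the particular values.

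**What to change.** - **SUVmax and PFS:** use a Cox model on continuous log SUVmax in the scanned patients, with hazard ratio and 95% CI, in place of a log-rank test at a cut-off.
- **SUVmax and lesion-level benefit:** use a method that accounts for lesions sharing a patient, for example GEE or a mixed model, in place of the plain t-test or Chi-square test.
- **Interpretation:** report the SUVmax result as an association with outcome in treated patients, not as treatment-specific prediction.
- **PFS:** state that the conclusion rests on the Kaplan-Meier median with 95% CI in the ITT set. Label any log-rank p-value an exploratory subgroup comparison and report how many were run. The plan is written in the past tense, so a list of subgroups added now may be post hoc; the exploratory label and the count are therefore needed in any case.

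Cost: wording and a few lines of code in the SAS version already named, with no extra patients or data. Lesion-level intervals may be wider. The number of scanned patients is not stated, so the precision of the Cox estimate is unknown and should be shown by its interval.

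### If the exploratory FES SUVmax analysis is done by lesion, as the single-lesion outcome definitions suggest, the only comparison tests named for it ignore clustering of lesions within patients

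*Combined protocol and SAP*

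**What the plan says.** The Study Endpoints section lists, as exploratory, the value of FES SUVmax for predicting efficacy of the study treatment. It does not say whether the unit is the patient or the lesion. Directly afterwards, with reference to RECIST 1.1, it states that "we defined the response evaluation criteria for a single lesion". It gives diameter rules for progression, response and stable disease of one lesion, and ends with a binary outcome: complete response, partial response, or stable disease of at least "6 months was defined as clinical benefit of a single lesion".

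The other response endpoints count patients. ORR is "the proportion of patients with complete response [CR] or partial response [PR] per RECIST version 1.1", and CBR is likewise a proportion of patients.

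The Statistical Analysis section names Kaplan-Meier estimation with log-rank tests for PFS. Its rule for measurements on a continuous scale is: "The comparison of continuous variables between two samples of normal distribution was performed by the t-test". For yes/no or grouped outcomes the same sentence adds a second rule, namely that "the comparison of the two categorical data was conducted with the Chi-square test". The significance sentence begins "For all analyses, a 2-tailed" and sets p ≤ 0.05. The plan names no method for several observations from one patient and does not mention within-patient correlation.

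**The concern.** A lesion-level outcome is defined, yet PFS, ORR, CBR and OS do not need it. The FES endpoint is the only listed endpoint without a stated unit, and the lesion definitions follow it directly, so it is their likely user.

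A natural analysis would then compare SUVmax between lesions with and without benefit (t-test), or benefit between high-uptake and low-uptake lesions (chi-square). Lesions in one patient share tumour biology, drug exposure and imaging conditions, so both uptake and outcome may well be alike within a patient. Treating the lesions as independent overstates the information. A chance association between uptake and benefit could then be declared significant more often than the stated 5%, and a candidate predictive marker would look better supported than it is.

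**Working it through.** **Inputs from the plan.** A binary outcome per lesion (Study Endpoints); t-test and chi-square, two-sided 0.05 (Statistical Analysis). The plan gives no number of patients with FES imaging, lesions per patient, within-patient correlation or SUVmax cut-off. Apart from the nominal 5% there is no figure to reproduce, and every input below is an assumption.

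**Step 1: formula.** With *m* lesions per patient, and within-patient correlations ρx for SUVmax and ρy for the outcome, the variance of the group difference under no association is inflated by about

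DE = 1 + (m − 1) · ρx · ρy,

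and the true size of the nominal 5% test is about 2 · [1 − Φ(1.96 / √DE)].

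- m = 1, or either correlation zero: DE = 1, size 5%.
- m = 2, both 0.3: DE = 1 + 1 × 0.09 = 1.09, size 6.1%.
- m = 3, both 0.5: DE = 1 + 2 × 0.25 = 1.50; 1.96/√1.50 = 1.60; size 11.0%.
- m = 5, both 0.5: DE = 1 + 4 × 0.25 = 2.00, size 16.6%.

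The product ρx · ρy shows that both correlations are needed.

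**Step 2: simulation.** No true association, 60% of lesions with benefit, a normal patient effect in SUVmax and in a latent outcome variable, the same correlation in both, 6000 runs per cell. The Monte Carlo standard error near 5% is √(0.05 × 0.95 / 6000) = 0.3 percentage points. Because the outcome correlation is on the latent scale, it is smaller on the yes/no scale, and sizes fall below the formula at the same nominal correlation.

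Size of the nominal 5% t-test:

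| Patients × lesions | Corr. 0.2 | Corr. 0.4 | Corr. 0.6 |
|---|---|---|---|
| 15 or 25 × 2 | 5.0% | 6.2–6.8% | 7.8–8.0% |
| 15 × 3 | 6.0% | 7.4% | 11.9% |
| 25 × 3 | 5.6% | 7.6% | 11.0% |
| 15 × 5 | 5.9% | 9.9% | 16.3% |
| 25 × 5 | 5.6% | 9.5% | 16.7% |

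The chi-square test with SUVmax split at the median has size 5.4% to 14.1% over the rows with 3 or 5 lesions. With unequal lesion counts (1 to 8, mean 3.1; 2000 runs) the t-test is at 5.1% to 15.1%.

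**Step 3: controls.** One lesion per patient: t-test 4.9% to 5.4%. One correlation zero and the other 0.6 (20 patients × 4 lesions): 5.2%. The inflation therefore comes from clustering in both variables.

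**Step 4: does the alternative hold its level?** Logistic GEE of lesion benefit on SUVmax, patient as cluster, 15 or 25 patients, 2000 runs per cell. With a small-sample-corrected robust variance (Mancl-DeRouen, or Kauermann-Carroll with a t reference) the size is 3.0% to 6.4% over equal and unequal lesion counts. With the uncorrected robust variance it is 6.3% to 10.3%, so the correction matters with so few patients.

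**The case against.** The strongest reply is that the fault is conditional. The t-test and chi-square sentences are generic and mention neither lesions nor FES, and the endpoint speaks only of efficacy. The inflation needs lesions as the unit, several per patient, these tests applied to them, and correlation in both variables. On this view the documented gap is only that the FES analysis is not specified. This stands as a limit on certainty: a reader might infer that the plan has committed itself to an invalid lesion-level test, and the text does not go so far. It does not remove the point. The plan defines a lesion outcome, names tests, and applies its 0.05 threshold to every analysis; carried out on that outcome, the named tests ignore patient.

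A second reply is that the effect may be negligible. Eligibility admits non-measurable bone-only disease, which diameter rules cannot score, so scorable lesions per patient may be few. This also stands: with 2 lesions and correlation 0.2 there is no visible inflation.

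A reader might also infer a larger inflation from the 6-month rule, if lesions still stable when the patient progresses early were all scored as no benefit. The documents do not support that step. The Interventions section says only that treatment runs until progression, and nothing says when lesion assessment stops or how such lesions are scored.

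**Conclusion.** The concern holds in a limited form. If the FES analysis uses lesions, the tests the plan names are too liberal whenever patients contribute several lesions and both SUVmax and outcome cluster by patient. Under the assumed 15 or 25 patients and correlations of 0.2 to 0.6, the nominal 5% t-test runs at about 5% to 8% with 2 lesions per patient and about 5.5% to 17% with 3 to 5. The top of that range needs 5 lesions and both correlations at 0.6; at correlation 0.2 the excess is at most about one percentage point. None of these inputs is in the documents, and the lesion unit is inferred.

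It would be wrong to read this as a doubt about the trial's main results. PFS, ORR, CBR, OS and safety are analysed by patient and are untouched. The point is minor, with medium confidence.

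**What to change.** 1. State the unit of the FES analysis and where the single-lesion definitions are used. If each patient contributes one SUVmax value, no change for clustering is needed.
2. If the lesion is the unit, replace the t-test and chi-square for lesion-level comparisons with an analysis that treats patient as the cluster. One example is logistic GEE of lesion benefit on log SUVmax with a small-sample-corrected robust variance; a mixed model is an alternative, though it was not simulated here. The uncorrected robust variance is not a good substitute with 15 to 25 patients.
3. Report the numbers of patients and lesions for each such analysis.

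The cost is a few sentences in the Statistical Analysis section and no new data. The plan already names "SAS version 9.4 (SAS Institute"), which has procedures for clustered data. The drawback is precision: in the simulations with 3 or 5 lesions per patient, the corrected interval for the log odds ratio was 8% to 16% wider than the naive one at correlation 0.2 and 30% to 53% wider at 0.6.
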